7.6.4 SUBJECT WITHDRAWAL

Subjects will be withdrawn from the study if:

- Subject is noted to be pregnant
- The subject may withdraw if he/she had a serious adverse event that is deemed either related to study device or procedures
- Subject voluntarily withdraws from study
- There is an infection at the sensor insertion site that has not responded to treatment within 3 days and subject has only one functional sensor
- Subject develops more than one instance of DKA or more than one instance of severe hypoglycemia which require stopping an accuracy visit.
- Investigator determines it is in Subject's best interest to withdraw.
- Subject is lost to follow-up
- Subject dies

7.6.5 STUDY EXIT

A Subject's participation is considered complete after the follow-up Visit post-Sensor removal. A Subject may choose to withdraw at any time without adverse effect on their care. The subject will continue with their medical follow-up, according to standard-of-care. The reason for study withdrawal will be documented.

In the event that a subject withdraws from the investigation or is lost to follow-up, the Investigator will make all reasonable efforts to locate a Subject and encourage Subject to return for Sensor removal. If a subject is lost to follow-up, three separate telephone calls should be made to attempt to schedule a follow-up visit or obtain follow-up information. All attempts and contacts should be documented in the source documents. The subject's Primary Care Physician may also be contacted as stated in the Informed Consent Form. If the Subject does not respond to the three telephone calls, then the Investigator will send a certified letter to the Subject. The Subject will be considered lost to follow-up if this communication is unsuccessful.

7.6.6 REPLACEMENT OF SUBJECTS

Subjects who exit the study prematurely may not re-enter the study and will not be

replaced.

7.7 STUDY STOPPING RULES

Senseonics may choose to suspend or prematurely terminate the investigation for the following reasons:

- Subject safety issue
- More than 3 subjects require withdrawal from the study due to Severe hypoglycemia or DKA
- Production limitation
- Administrative decision

The Medical Monitor will review adverse events on a scheduled periodic basis as outlined in Section 13.13. In the case of device-related serious adverse events, the Medical Monitor will consult with the Sponsor and Principal Investigator if appropriate to ensure that the necessary steps are taken to protect the safety and well-being of the Subjects.

In the event that that study is stopped, the Investigator will promptly inform the Subjects and ensure appropriate therapy and follow-up, including Sensor removal. Additionally, the investigator will promptly inform the IRB and provide a detailed written explanation. The pertinent regulatory authorities will be informed according to local regulations.

7.8 TERMINATION OF INVESTIGATOR OR INVESTIGATIONAL SITE

Senseonics reserves the right to terminate an investigator/investigational site for any of the following reasons, which are considered major deviations:

- Failure to secure subject informed consent including protection of personal data prior to enrollment
- Failure to report unanticipated adverse device effects and serious adverse events to Senseonics and to the IRB within its required reporting time after learning of the event
- Repeated investigational plan deviations
- Loss of or unaccounted for investigational product inventory.

8 RISK AND BENEFIT ANALYSIS

8.1 POTENTIAL BENEFITS

Studies have shown that real-time CGM use improves patients overall glycemic control.¹⁰ Improved glycemic control may not be achieved by all subjects. However, subjects are contributing to the overall advancement of medical and scientific knowledge that may benefit future subjects with similar conditions. The CGM data collected will not be used for any clinical decisions or care.

8.2 POTENTIAL RISKS

The Eversense® CGM System has been approved for measuring interstitial fluid glucose for up to 90 days by FDA in June 2018. However, the Eversense® 180 CGM System for measuring interstitial fluid glucose for up to 180 days is considered investigational in the United States. To evaluate the Eversense® 180 CGM system, blood draws for glucose measurements will be performed more frequently than in daily routine. In addition to use of the System, hyperglycemia and hypoglycemia challenges may be performed exclusively for study purposes.

8.3 ANTICIPATED ADVERSE EFFECTS

The following adverse effects could occur in association with insertion, removal, and/or use of the Eversense® 180 CGM System Sensor and/or Transmitter:

- Infection, local or systemic, possibly resulting in sensor removal
- Excessive bleeding during insertion or removal
- Bruising or swelling
- Poor wound healing after insertion or removal
- Keloid and/or scar formation
- Excessive or prolonged pain or discomfort at the Sensor site
- Nerve damage causing tingling, numbness, pain or weakness
- Uncomfortable heating
- Burn
- Electrostatic shock
- Skin irritation and/or redness
- Itch
- Discoloration of skin
- Skin thinning
- Hematoma formation
- Device migration
- Skin erosion

- Allergic reaction to the device components, local anesthetic, or other medication or materials used in the procedure
- Anxiety and/or nervousness and/or lack of sleep
- Device fragments or particulate matter remaining in the body
- Failure to retrieve device or device left behind
- Difficulty in removing device that may require surgery
- Device malfunctions of the Sensor and/or Transmitter with possible need to remove and/or replace the Sensor and/or Transmitter
- Burning sensation or pain.
- Elevated blood pressure
- Water retention in the tissue, swelling or edema
- Airway spasms
- Shortness of breath
- Circulatory disorders
- Confusion
- Disorientation
- Increased or decreased sensitivity to touch or pain
- Metallic taste
- Sleepiness
- Visual disturbances and/or blurred vision
- Tinnitus
- It is possible that the local anesthetic could cause a reaction other than listed or previously seen.
- Fluid/electrolyte disturbances such as fluid retention
- Muscle weakness
- Osteoporosis
- Peptic ulcer
- Pancreatitis
- Ulcerative esophagitis
- Impaired wound healing
- Headache
- Psychic disturbances and mood swings
- Convulsions
- Glaucoma

- Weight gain
- Nausea and/or vomiting
- Malaise
- Irritability
- Insomnia
- Heartburn
- Hyperglycemia
- Ketosis
- Headaches
- Dizziness, lightheadedness, and/or fainting
- It is possible that the use of the Eversense® 180 CGM system could cause a reaction other than listed or previously seen.
- It has not been determined whether the risks usually associated with injectable dexamethasone apply to the use of dexamethasone elution ring, a highly localized, controlled-release device.
- The dexamethasone ring could cause other adverse events not listed or previously seen.
- Other adverse events typically related to diabetes treatment and diabetes are unknown

8.4 RESIDUAL RISKS ASSOCIATED WITH THE INVESTIGATIONAL DEVICE

Components of the Eversense® 180 CGM System are manufactured under the Quality System provisions of ISO 13485:2016.

Risk analysis has been performed and adequate control put in place as prescribed in relevant provisions of IEC 62304, ISO 14971, and IEC 60601-1, in accordance with the requirements of ISO 13485:2016. Residual risks associated with the device included risks in the categories of electromagnetic and thermal energy, biocompatibility, biologic, chemical and mechanical factors, and user-related error. All identified risks have been reduced as far as possible using various control methods including software revision and re-validation, hardware design modification, packaging and sterilization process validation and labeling revision. The calculated residual risks were determined to be acceptable for conduct of this clinical investigation.

8.5 RISKS ASSOCIATED WITH PARTICIPATION IN THE CLINICAL INVESTIGATION

This clinical investigation involves subjects with diabetes mellitus. These subjects may experience hyperglycemia and hypoglycemia as a consequence of their existing condition and medical management (e.g. insulin administration). For this study, hyperglycemia and hypoglycemia will not be reported as adverse events unless meeting criteria of a Serious Adverse Event. Episodes of hyperglycemia and hypoglycemia as documented by the Subject SMBG Meter will be reported in an extra listing separate from the AE listings. Should a known side effect(s) occur to administered medication(s) used in the intervention, such effects will be reported as part of the adverse event description and will not be considered a separate adverse event.

The amount of blood drawn for in-clinic testing during the study is below the acceptable limits of blood donation of approximately 475 mL per 8 weeks; hence it does not pose any additional unacceptable risk to the subjects.

This clinical investigation involves the following procedures that present risk: placement of an intravenous catheter, frequent blood sampling, and conduct of hyperglycemia and hypoglycemia challenges at the clinic visits. In addition, Subjects in this study may use an insulin pump or syringes to administer subcutaneous insulin.

The following risks are potentially associated with such procedures:

- Routine administration of insulin may cause hematoma, redness, swelling and itch at the injection site, skin rash, itch, sweating, gastro-intestinal complaints, edema, difficulty breathing, palpitations and drop in blood pressure, and even death.
- Hypoglycemic symptoms requiring medical intervention which may include seizures, neuroglycopenia, coma and even death (including occurrence during home use)
- Insulin administration leading to hypoglycemia include: cold sweating, cool and pale skin, fatigue, nervousness, shakiness, anxiety, weakness, confusion, feeling of numbness, hunger, impairment of vision, problems with concentration, headache, nausea, palpitations, coma, or death.
- Hyperglycemia and diabetic ketoacidosis requiring medical intervention which may include potential complications such as nausea, vomiting, abdominal pain, dehydration, difficulties with breathing, confusion, bad breath, low blood pressure, coma, kidney failure, cardiac arrhythmia, myocardial infarction, cerebral edema, rhabdomyolysis and even death (including occurrence during home use).
- Excessive pain during insertion of the IV catheter
- Multiple sticks due to IV placement

- IV placement failure
- Restricted mobility
- Fainting, dizziness, lightheadedness or low blood pressure in response to blood sampling
- Bleeding during catheter insertion or infusion pump infusion set change
- Bruise formation at catheter site or due to infusion pump use
- Fluid overload due to saline flushes of IV catheter
- Skin redness or scarring due to infusion pump use
- Temporary muscle or nerve irritability, arrhythmia or death due to electrolyte disturbance
- Tissue damage (burn) due to heating devices
- Severe gastro-intestinal distress
- Difficulty breathing
- Cardiovascular symptoms
- Nerve damage
- Rash
- Pain
- Infection, local or systemic
- Blood clots, which may cause inflammation, swelling and pain
- Circulatory disorders, including but not limited to low blood pressure
- Skin irritation or pruritus due to medical adhesive (electrodes, tapes, etc.)
- Infection, inflammation or phlebitis at IV insertion sites or infusion pump infusion set sites
- Edema at the insertion site
- Erythema at the insertion site
- Allergic reaction
- Excessive pain or burning sensation associated with injections
- Headache
- Vasovagal response or fainting
- Anemia due to blood sampling

Subject may have an X-ray or ultrasound of the sensor site. X-rays may cause damage to cells in the body, which in turn may increase the risk of developing cancer. This increase

in risk associated with each X-ray procedure is extremely low but does slowly increase with the increasing number of X-rays tests you have.

Even though there are no known risks of ultrasound imaging, it can produce effects on the body. When ultrasound enters the body, it heats the tissues slightly. In some cases, it can also produce small pockets of gas in body fluids or tissues (cavitation). The long-term effects of tissue heating, and cavitation are not known.

8.6 POSSIBLE INTERACTIONS WITH CONCOMITANT MEDICAL TREATMENTS

The transmitter is incompatible with magnetic resonance imaging (MRI) procedures. The transmitter is MR Unsafe and must be removed before undergoing an MRI procedure. Before undergoing an MRI procedure, the subjects should contact the study staff. Subjects should also let the MRI staff know that they have a sensor and transmitter.

The sensor is MR conditional and subjects can be safely scanned in an MR system meeting the following conditions:

- Static magnetic field of 1.5T or 3.0T
- Maximum spatial field gradient of 2000 gauss/cm (20 T/m)
- Maximum MR system reported, whole body averaged specific absorption rate (SAR) of 4 W/kg (First Level Controlled Operating Mode)

8.7 DEXAMETHASONE

It has not been determined whether the risks usually associated with injectable dexamethasone apply to the use of dexamethasone elution ring, a highly localized, controlled-release device.

8.8 ELECTROSTATIC SHOCK

The external device (Transmitter) has been tested and passed the Electrostatic Discharge (ESD) test according to IEC 61000-4-2:2008 air and contact immunity test levels in accordance with IEC 60601-1-2:2014 EMC collateral standard. No known damage to the external device or to the overall CGM system has been observed as documented in the EMC report.

8.9 EFFORTS TO MINIMIZE RISK

This investigation will be conducted by investigators who are qualified by training and experienced in the treatment of diabetes mellitus and specifically in the execution of hyperglycemia and hypoglycemia challenges. In the event of a clinical emergency,

detailed safety plans will be in place at each clinical site for monitoring and the management of clinically significant hypoglycemia and hyperglycemia. A full resuscitation cart with defibrillator, and staff trained in the care of diabetes and cardiac emergencies will be present at site. A nurse, nurse practitioner or physician/PA will be present at the bedside or unit at all times. A study physician/PA or nurse practitioner will be present during the hypoglycemia and hyperglycemia challenge times.

In addition, adequate measures including eligibility criteria limitations, subject screening and pre-visit assessment of the subject's diabetes status have been incorporated into the clinical investigation with the intention of minimizing such risks.

Investigators will be trained in the technique for Sensor insertion and removal. Investigators will examine the insertion site during each in-clinic visit and document any suspected adverse event. Subjects will be instructed to contact the investigator immediately upon any sign of significant irritation or discomfort or evidence of infection as described previously. In addition, an independent medical monitor will review safety related aspects of the investigation including review of serious adverse events and unanticipated adverse device effects.

Furthermore, potential risks associated with participation in this investigation will be minimized and managed in accordance with 21 CFR Part 812, ISO 14155¹¹, regulations by local regulatory authorities and requirements of the approving Investigational Review Boards.

8.10 RISK TO BENEFIT RATIO

The Sponsor believes that any potential risk presented by this investigation has been minimized and that adequate testing, safeguards, and safety monitoring have been incorporated into the investigation to further minimize and mitigate the risks.

The Sponsor believes that the value of the knowledge to be gained by conducting this clinical investigation to demonstrate the safety and accuracy of the Eversense® 180 CGM System outweighs the potential risks posed to participating subjects.

All potential study Subjects will sign an informed consent form and conduct a discussion with delegated investigative personnel concerning the risks and benefits of participating in the clinical trial.

9 ADVERSE EVENTS

The following are definitions and requirements for adverse event monitoring and reporting. The definitions and requirements of local regulations will be followed if different from below.

The name and telephone number of the individual for the Site to contact regarding safety issues is listed in the General Information and Contacts section in the front of the protocol. Subjects will contact the Investigator with any questions or concerns. The Investigator will contact Senseonics with questions regarding recording and reporting of adverse events.

9.1 ADVERSE EVENT DEFINITIONS

Adverse Event (AE) is defined as any untoward medical occurrence, unintended disease or injury, or untoward clinical signs (including abnormal laboratory findings) in subjects, users or other persons, whether or not related to the investigational medical device.

NOTE 1: This definition includes events related to the investigational medical device or the comparator.

NOTE 2: This definition includes events related to the procedures involved.

NOTE 3: For users or other persons, this definition is restricted to events related to investigational medical devices.

Serious Adverse Event (SAE) is defined as an adverse event that:

- Leads to death;
- Leads to a serious deterioration in the health of the Subject that either:
 - Results in life-threatening illness or injury; or
 - Results in a permanent impairment of a body structure or a body function; or
 - Requires inpatient or prolonged hospitalization; or
 - Results in medical or surgical intervention to prevent life-threatening illness or injury or permanent impairment to a body structure or a body function;
- Led to fetal distress, fetal death or congenital abnormality or birth defect;

NOTE: Planned hospitalization for a pre-existing condition, or a procedure required by the CIP, without serious deterioration in health, is not considered a serious adverse event.

Anticipated adverse events are AEs that have been identified as possible adverse events related to the investigational device or procedure.

Unanticipated adverse device effects (UADEs) are defined as any serious adverse effect on health or safety or any life-threatening problem or death caused by, or associated with, a device, if that effect, problem, or death was not previously identified in nature, severity, or degree of incidence in the investigational plan or application (including a supplementary plan or application), or any other unanticipated serious problem associated with a device that relates to the rights, safety, or welfare of study subjects.

Severity

Mild: Awareness of a sign or symptom that does not interfere with the Subject's usual activity or is transient, resolves without treatment and with no sequelae

Moderate: Interferes with the Subject's usual activity and/or requires symptomatic treatment

Severe: Symptom(s) causing severe discomfort and significant impact on the Subject's usual activities and/or requires treatment

Causality: The causal relationship should be determined with respect to the investigational device, the insertion or removal procedure, or other study-related procedures.

None: The event is not associated with the device or procedure. There is no relation between the event and the device or procedure.

Possibly Related: The temporal sequence between the device or procedure and the event is such that the relationship is not unlikely or there is no contradicting evidence that can reasonably explain the Subject's condition. There is a possibility of any relation between the event and the device or procedure.

Related: The temporal sequence is relevant, or the event abates upon device application completion/removal or the event cannot be reasonably explained by the patient's condition or comorbidities. The event is related or most likely associated with the device or procedure.

Unknown: There is no evidence or relevant data available to assess the relationship between the event and the device or procedure.

9.2 MONITORING ADVERSE EVENTS

Adverse events (AEs) may be volunteered by Subjects, elicited by Investigator or others, or observed. All AEs will be assessed by the Investigator who will determine whether or not the event is related to the device, and/or insertion or removal procedure or other study-related procedure. The Investigator will determine whether or not the event meets the

serious criteria. If it is determined that an AE has occurred, the Investigator should obtain all the information required to complete the reporting process, including source documentation.

9.3 ADVERSE EVENT REPORTING

All adverse events (AEs) will be reported by the Investigator and reviewed by the Sponsor in compliance with applicable regulations. Site will follow local IRB reporting requirements for reporting to IRB.

All SAEs must be reported to Sponsor as soon as possible but in no event later than 3 days after learning of the event. Include Study ID, Study Site, Adverse Event, causal relationship to device and procedure (insertion/removal/other study procedure), seriousness, expectedness, and provide source documentation as soon as available. The AE form of the CRF must be completed within 3 days of awareness for all SAEs.

All UADEs must be reported to the Sponsor and to the reviewing IRB as soon as possible, but in no event later than 3 days after the Investigator first learns of the event. The AE form of the CRF must be completed as soon as possible but no later than 3 days for all UADEs.

All adverse events classified as possibly related or related to the device or procedure will be reported to Senseonics as soon as possible but no later than 3 days of learning of events.

9.3.1 AE REPORTING PERIOD

Adverse events are reported from enrollment until study participation has ended. Adverse events related to the device or procedure will be followed until resolution, AE has stabilized, or the study has been completed.

9.3.2 PRE-EXISTING MEDICAL CONDITIONS

Pre-existing medical conditions or symptoms reported prior to enrollment will not be recorded as an AE. In the event there is a change in the pre-existing medical condition or symptoms due to the device or study-related procedure, then an AE must be recorded.

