11.2 SAFETY ENDPOINTS

The safety endpoint is the incidence of device-related or insertion/removal procedure-related serious adverse events (SAEs) in the clinic and during home use through 180 days post-insertion.

An Adverse Event is considered 'related' if the relatedness is categorized as 'possibly related', or 'related'. The assessment of seriousness and relatedness made by the Medical Monitor will be used for analysis. The numbers of SAEs and the percentage of patients with SAEs will be reported for each SAE type that is observed, identified as device-related, procedure-related or unrelated to the study (Table 3 in APPENDIX 1). The count and proportion of patients experiencing at least one device-related or procedure-related SAE will be presented. No inferential statistical analysis will be performed.

Other safety endpoints include:

- Incidence of insertion/removal procedure or device-related adverse events in the clinic and during home use.
- Incidence of all adverse events in the clinic and during home use.
- Incidence of hospitalizations due to hypoglycemia, hyperglycemia or ketoacidosis occurring during home use.

- Incidence of reported hypoglycemic and hyperglycemic events occurring during home use.

For each of the adverse event (AE or SAE) categories above, the numbers of AEs and the percentage of patients with AEs will be reported for each AE type that is observed and be stratified by the target age enrollment categories (Tables 4A-4E in APPENDIX 1). A listing (Table 5 in APPENDIX 1) will be prepared that identifies each patient with a reported AE or SAE, and relevant information including date of onset, severity level, seriousness, relatedness to the device or procedure, classification as anticipated or unanticipated, corrective action(s) taken, and resolution status (resolved or ongoing).

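### Protocol 9.3.2 names device or procedure causation as its only trigger for recording a change in a pre-existing condition, so non-serious worsening that the site attributes elsewhere can be lost before adjudication

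*Protocol*

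**What the plan says.** Protocol 9.3.2 has two sentences. The first is a general exclusion: "Pre-existing medical conditions or symptoms reported prior to enrollment will not be recorded as an AE". The second gives the one stated case in which a change is recorded, namely "a change in the pre-existing medical condition or symptoms due to the device or study-related procedure, then an AE must be recorded". Nothing is said about a change that the site puts down to another cause, and nothing about seriousness.

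Elsewhere the Protocol treats cause as something graded after an event is recorded:

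- 9.1 defines an AE as an untoward occurrence "in subjects, users or other persons, whether or not related to the investigational medical device", and offers four causality grades: none, possibly related, related and unknown.
- 9.2 has the site grade events that already count as AEs: "All AEs will be assessed by the Investigator who will determine whether or not the event is related to the device".
- 9.3 requires all AEs to be reported and sets a deadline for serious ones: "All SAEs must be reported to Sponsor as soon as possible but in no event later than 3 days after learning of the event".
- 11.2 lists among the other safety endpoints "Incidence of all adverse events in the clinic and during home use", and says of the analysis: "The assessment of seriousness and relatedness made by the Medical Monitor will be used for analysis". SAP 6.6.1 agrees. Both count a grade of possibly related as related.
- 13.13 makes the Medical Monitor responsible for assigning the relatedness used in the endpoint.

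**The concern.** Following 9.3.2 as written, a site decides causality before the event exists in the data. If it decides against the device, the section gives no instruction to record the worsening. The all-AE endpoint, which is meant to be independent of cause, then depends on a site causality judgement for this class of event. The related-AE endpoint can also lose events, because the Medical Monitor cannot grade what was never entered.

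The early judgement is a hard one here. The sensor elutes dexamethasone, and Protocol 8.7 says it is not known whether the risks of the injectable drug carry over. The anticipated effects in 8.3 include elevated blood pressure, glaucoma, osteoporosis, peptic ulcer and mood swings, several of which adults with diabetes may already have. The entry criteria in 3.2.2 admit blood pressure up to 160/100 mm Hg and, with clearance, asymptomatic coronary disease. Worsening of such a condition is easily ascribed to the underlying disease.

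The safety evidence is a set of descriptive counts from a study with no control device. Under-recording can only lower those counts.

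**Working it through.** The plan states no figure on this point, so the check is mainly a comparison of texts.

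**1. Is the exclusion written or implied?** 9.3.2 says that a change of one kind must be recorded. It does not say that other changes must not be. The exclusion follows from a general rule of non-recording plus a single stated exception. That is the natural reading, but it is an inference.

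**2. Is the trigger the same as the endpoint's test?** No. 9.3.2 asks whether the change is due to the device or procedure. 9.1 allows a grade of possibly related where a link is merely not unlikely, and 11.2 counts that grade as related. A worsening that the site would grade only possibly related, or unknown, may not meet the 9.3.2 trigger. So the filter can catch more than events the site considers plainly unrelated.

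**3. Order of steps.** Under 9.1, 9.2 and 13.13: event, record, site grade, Medical Monitor grade, analysis. Under 9.3.2, for pre-existing conditions: event, site attribution, then record only if attributed. The two orders disagree.

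**4. Serious worsening.** Two chains can be built.
- By 9.1 a serious worsening is an AE whatever its cause, hence an SAE, and 9.3 requires all SAEs to be reported. 11.2 tabulates SAEs unrelated to the study. The note under 9.1 on planned hospitalization for a pre-existing condition turns on deterioration, not on cause.
- Against that, 9.1 begins "Serious Adverse Event (SAE) is defined as an adverse event that", so an event that is not an AE cannot be an SAE. 9.3.2 also has no seriousness exception, although 9.3.3, on hypoglycemia and hyperglycemia, does.

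The first chain has more support. The second is enough to make the text ambiguous. Serious glycemic events are protected by 9.3.3 and, when they lead to hospitalization during home use, by a separate endpoint in 11.2.

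**5. Size, all-AE count.** Among AEs that a cause-independent rule would record, let w be the share that are worsening of known disease, u the share of those not attributed by the site to the device or procedure, and h the share of those actually withheld. Then

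proportion of AEs lost = w × u × h ≤ w.

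The documents give none of the three. If w is assumed to be 10% to 30%, the loss reaches 10% to 30% only when u = h = 1. If u × h = 0.5, also an assumption, it is 5% to 15%. Worsening that the site does attribute is recorded, so u = 1 is an extreme. The percentage of subjects with any AE falls only for subjects who have no other recorded AE.

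**6. Size, main SAE endpoint, if one related event were lost.** With about 180 inserted subjects (Protocol 3.3.1), one subject is 1/180 = 0.56 percentage points. The exact two-sided 95% upper limit is 1 − 0.025^(1/180) = 2.03% for 0 of 180 and, by the same Clopper-Pearson method, 3.06% for 1 of 180. The Protocol sets no safety threshold and plans no inferential safety analysis, so this describes scale and changes no decision rule.

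**The case against.** The strongest reply is that 9.3.2 only fixes the baseline: a condition present at enrollment is not itself an AE. On that view the second sentence adds a duty for related changes, and 9.1, 9.2 and 9.3 still govern everything else. There are also other routes to detection. Subjects are told to report hospitalizations and significant medical changes (4.2.5), sensor sites are examined at each clinic visit (7.3), the sponsor reviews source documents and queries possible AEs (10.1), and the Medical Monitor sees medical safety data and laboratory values (13.13). The Safety Management Plan and the data-entry guideline may say more, but they are not among the documents.

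Part of this stands. The restrictive reading is implied rather than stated, and some omissions would be caught. But a site that left out an unattributed worsening would appear compliant with 9.3.2, so review against the Protocol would not reliably flag it.

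A reader might also infer that serious worsening judged unrelated by the site definitely drops out of the main safety endpoint. The documents do not support that. 9.3 requires every SAE to be reported, and 11.2 expects unrelated SAEs in the tables. For the main endpoint to lose an event, it would have to be serious, be a worsening of known disease, not be attributed by the site, be graded at least possibly related by the Medical Monitor had it been seen, and be withheld despite 9.3.

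Nor can it be inferred that the all-AE loss equals the whole share of worsening events, or that all AEs in subjects with a comorbidity are filtered. Attributed worsening is recorded, and new-onset events are untouched.

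**Conclusion.** The concern holds for non-serious worsening. Read naturally, 9.3.2 contradicts 9.1, 9.3 and 11.2, and a site that follows it can leave such events out of the all-AE and related-AE endpoints and out of adjudication. The direction is known: any loss favours the device. The size is not. It is bounded by the product in step 5 of the working, and the percentages there rest on assumed shares.

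For serious worsening the Protocol is ambiguous rather than permissive. Loss from the main safety endpoint is possible but unlikely.

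The conclusion assumes that sites take 9.3.2 as a recording rule and that no unseen guideline overrides it. This is a wording conflict that needs reconciling, not evidence that events have been missed.

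**What to change.** Replace the second sentence of Protocol 9.3.2 with text to this effect: any worsening after enrollment in the severity, frequency or seriousness of a pre-existing condition is recorded as an AE regardless of suspected cause; worsening that meets the SAE criteria is always reported as an SAE under 9.3; relatedness is then graded under 9.1 and adjudicated by the Medical Monitor under 13.13. Keep the first sentence as the rule for the condition as it stood at enrollment, and carry the same wording into the site AE instructions.

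For subjects already inserted, check existing source notes for worsening that was not recorded under the current wording, enter what is found, and send it for adjudication.

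The cost is a short protocol change and a small amount of site work. The reported AE rate may rise slightly. No visit, procedure or treatment changes.
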